4.2 Study Endpoints

4.2.1 Phase 1 Study Endpoints

Phase 1 Primary Endpoint:

- Area Under the Curve (AUC), Sensitivity, and Specificity of VCI when compared against standard of care CTA imaging for large vessel occlusion assessment.

Phase 1 Secondary Technical Efficacy Endpoint:

- Area Under the Curve (AUC), Sensitivity, and Specificity of a novel machine learning (ML) algorithm when compared against standard of care CTA imaging for large vessel occlusion assessment.
- VCI and experimental ML algorithm compared to prehospital/neurological clinical scales for alternative diagnostic criteria.

Phase 1 Primary Safety Endpoint:

- Incidence of device-related serious adverse events
- Last Known Normal (LKN) to First Hospital Arrival (Initial Door-In) time
- Door to Initial CT imaging (non-contrast) time
- Door to IV-tPA time
- Door to Initial CTA Acquisition time
- Door to Groin Puncture time
- CTA Acquisition to Groin Puncture time

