4.2.2 Phase 2 Study Endpoints

Phase 2 Primary Endpoint:

- Area Under the Curve (AUC), Sensitivity, and Specificity of VCI when compared against standard of care CTA imaging for large vessel occlusion assessment.

Phase 2 Secondary Technical Efficacy Endpoint:

- Area Under the Curve (AUC), Sensitivity, and Specificity of a novel machine learning (ML) algorithm when compared against standard of care CTA imaging for large vessel occlusion assessment.

- VCI and experimental ML algorithm compared to prehospital/neurological clinical scales for alternative diagnostic criteria.

Phase 2 Primary Safety Endpoint:

- Incidence of device-related serious adverse events
- Last Known Normal (LKN) to First Hospital Arrival (Initial Door-In) time
- Door to Initial CT imaging (non-contrast) time
- Door to IV-tPA time
- Door to Initial CTA Acquisition time
- Door to Groin Puncture time
- CTA Acquisition to Groin Puncture time

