4.9 Randomization

Randomization will occur once subject has satisfied all inclusion/exclusion criteria and informed consent has been obtained. Subjects will be randomly assigned in equal number (1:1) to one of two procedure arms within each cohort: 1) TCD Exam or 2) No TCD Exam. The number of procedures and controls will be balanced within investigational sites, by baseline NIHSS severity (≤ 17 versus >17), age (<70 years versus ≥ 70 years at the time of randomization) occlusion location (M1 versus all other), and time of day of initial CT scan (0900-1700 and 1701-0859). Subject allocation to procedure will be accomplished by using an interactive web response (IWRS) or interactive voice response system (IVRS).

At the time of randomization, the site will access IVRS/IWRS and enter subject's screening NIHSS, age, occlusion location, and time of CT scan. Based on the information provided, the system will automatically generate the assigned treatment. If the site is unable to access website for randomization, an interactive voice response randomization is also available by phone.

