4.16.2 Lucid M1 System Scanning Technique (Traditional TCD)

If traditional TCD is conducted using the Lucid M1 System alone, measurements will be collected in the MCA at multiple depths ranges between 45 to 65 mm. The MCA scans will be collected from the trans-temporal window by positioning the probe superior to the zygomatic arch. Once cerebral blood flow velocity (CBFV) of the target vessel is found, the TCD operator will hold this position to record 30 seconds of data.

Cohort A TCD will be subjects identified per CTA findings in the Emergency Room (ER), Stroke Care Unit or Imaging Unit as having a large vessel occlusion. A single TCD scan will be collected by a designated TCD operator using the NovaGuide System or the Lucid M1 System alone (manual TCD). The TCD scan will be collected following CTA within a three (3) hour window and prior to standard of care stroke treatment (e.g., mechanical thrombectomy). Note, tPA can be administered prior to TCD measurements. Study measurements will not delay nor interfere with the patients' standard of care treatment. No follow-up scans will be collected.

Cohort B TCD will be subjects identified per CTA findings in the Emergency Room (ER), Stroke Care Unit or Imaging Unit as having a non-large vessel occlusion. A single TCD scan will be collected by a designated TCD operator using the NovaGuide Robotic System or the Lucid M1 System alone (manual TCD). These scans will be collected within a 24-hour period after enrolment and no follow-up scans will be collected.

Cohort C NO TCD will be subjects identified per CTA findings in the Emergency Room (ER), Stroke Care Unit or Imaging Unit as having a large vessel occlusion. No TCD scans will be conducted and subjects followed through to discharge.

Cohort D NO TCD will be subjects identified per CTA findings in the Emergency Room (ER), Stroke Care Unit or Imaging Unit as having a non-large vessel occlusion. No TCD scans will be conducted and subjects followed through to discharge.

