In this work, we will also measure “Get with the Guidelines, Stroke” metrics from each site and compare them to literature, national and site metrics. This will enable us to demonstrate that the system does not adversely affect standard of care for subjects suspected of stroke. The reason we believe it will not affect standard of care is because the device will be used after initial CT and IV-tPA is administered, while the subject is waiting for CTA or intervention. The time window, although short, is available to allow us to measure both the TCD waveform and CTA to confirm VCI is an effective biomarker. Additionally, the times will be compared against the randomized groups (Cohort C and D).

Door to diagnostic imaging. (Statistical demonstration that show we will not delay anything when adding our NovaGuide workflow to), e.g. “Get with the Guidelines, Stroke”: We will calculate the following for subjects that have NovaGuide measurements:

- IV rt-PA arrive by 2 hour, treat by 3 hour: Percent of acute ischemic stroke patients who arrive at the hospital within 120 minutes (2 hours) of time last known well and for whom IV t-PA was initiated at this hospital within 180 minutes (3 hours) of time last known well.
- % Door to CT \leq 25 minutes: Percent of patients who receive brain imaging within 25 minutes of arrival.
- Door to Puncture (DTP) Time within 90 minutes: (Percentage of patients with acute ischemic stroke who receive mechanical endovascular reperfusion)

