11.2 Phase 2 Statistical Analysis

Primary Endpoint Analysis: Demonstration of VCI biomarker performance at or exceeding 90% ROC-AUC (targeting SEN & SPE greater than 90%) to standard of care imaging across multiple centers.

Here, we will determine the final biomarker performance using the dataset collected and reviewed by the core lab. Similar analyses will be run on the VCI biomarker distributions for the Phase 2 subject group as was done in Phase 1. Additionally, subgroup analyses comparing biomarker results across research sites, and age groups, will be conducted to determine if any age or NovaGuide inter-operator variability effects are present in the data (two-way ANOVA with post-hoc comparisons).

Sample size calculation: In Phase 2, we seek to demonstrate stricter confidence bounds on biomarker diagnostic performance in excess of 90% ROC-AUC. Assuming the biomarker is observed to meet that performance threshold, then a sample of approximately 150 LVO subjects in each patient group is required to attain a one-tailed 95% confidence bound on the observed AUC of 3%. That is, the target AUC and sample size would afford 95% confidence that the underlying general population AUC is greater than 87%. Moreover, across five sites, this results in approximately 30 LVO subjects per site, affording sufficient power for detection of moderate potential inter-site effects in the range of Cohen’s $D \geq 0.75$.

Calculate study and site specific stroke workflow times: Stroke workflow parameters and times are well characterized in literature, including “Get with the Guidelines, Stroke” published by the American Heart Association, Inc. and will be utilized as a historical control comparator for data collected in Phase 2. We will use these published stroke guidelines which have mean times for the stroke workflow parameters to show that we are non-inferior to these when using the NovaGuide device. Additionally, the data will be compared to the corresponding randomized group (Cohort C and D)

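### The groin-puncture safety times are defined only for punctured subjects, and the plan does not say how randomised LVO subjects without a puncture are counted

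*Combined protocol and SAP*

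**What the plan says.** Sections 4.2.1 and 4.2.2 list "Door to Groin Puncture time" and "CTA Acquisition to Groin Puncture time" under the primary safety endpoint of each phase. Section 11.1 explains that the workflow times are there to show that the device does not harm standard care. It introduces its guideline metrics with "We will calculate the following for subjects that have NovaGuide measurements", and one of them is "Door to Puncture (DTP) Time within 90 minutes: (Percentage of patients with acute ischemic stroke who receive mechanical endovascular reperfusion".

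Two comparisons are planned. One is with outside benchmarks, where section 11.2 aims "to show that we are non-inferior to these when using the NovaGuide device". The other is internal: "Additionally, the times will be compared against the randomized groups (Cohort C and D" (section 11.1, repeated in substance in 11.2). Allocation is randomised: "Subjects will be randomly assigned in equal number (1:1) to one of two procedure arms within each cohort" (section 4.9). For LVO subjects, section 4.16.2 states "The TCD scan will be collected following CTA within a three (3) hour window and prior to standard of care stroke treatment".

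The documents do not say how a randomised LVO subject who never has a groin puncture enters these analyses. They contain no puncture-rate endpoint by arm, no failure or competing-event rule, and no statement that the times are analysed by assigned arm.

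**The concern.** A puncture time is observed only if the puncture takes place. That event comes after randomisation and, in the TCD arm, after the scan, so the scan could affect whether it happens. The subject most harmed by a delay is one who loses thrombectomy, and that subject has no time to contribute. If the lost subjects would have been slower than average, as loss through running out of time implies, their absence also shortens the mean of those who remain. Either way, a lost thrombectomy is not counted as harm.

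The restriction to subjects with NovaGuide measurements is a second selection after randomisation. It can drop subjects whose scan was abandoned for lack of time. Read literally, it also drops those scanned with the Lucid M1 alone, which section 4.16.2 permits. With both selections, the comparison with Cohort C is no longer between the groups that were randomised. What is at stake is the claim that scanning does not delay care.

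**Working it through.** **Planned figures.** The documents give no sample size, margin, power or thrombectomy rate for the workflow comparison, so there is no figure on this point to reproduce. The sizing figures in sections 11.1 and 11.2 are diagnostic, and they do reproduce:
- Cohen's d of 1.25 (two-sided 0.05, 80% power) needs 11 per group.
- With the Hanley-McNeil standard error, the one-sided 95% bound is 1.645 x 0.0391 = 0.064 at AUC 0.85 with 50 per group.
- It is 1.645 x 0.0185 = 0.030 at AUC 0.90 with 150 per group.

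None of these covers puncture times.

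**Which workflow times can show a scan effect.** CTA is an entry criterion (section 4.6) and randomisation follows eligibility (section 4.9). Onset-to-arrival, door-to-CT and door-to-CTA are therefore fixed before allocation. IV-tPA may precede the scan (section 4.16.2). The two puncture times are the main listed times that can reveal a delay. They concern Cohort A (LVO, TCD) against Cohort C (LVO, no TCD): 54 against 54 in Phase 1 and 156 against 156 in Phase 2.

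**Illustrative model (assumptions, not from the documents).** Control puncture times are log-normal with median 60 min and log-SD 0.5. Each TCD subject takes 5 min longer. Five percent of TCD subjects are never punctured (0.05 x 156 = 7.8, about 8 in Phase 2).

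With nobody lost:
- Control mean = 60 x exp(0.5²/2) = 67.99 min. TCD mean = 72.99 min. Difference +5.0.
- Within 90 min: control Φ(ln(90/60)/0.5) = 79.1%; TCD Φ(ln(85/60)/0.5) = 75.7%.

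Three ways of losing the 5%:
1. *Same time cutoff in both arms.* Cutoff = 60 x exp(0.5 x 1.645) + 5 = 141.6 min. Controls kept = Φ(ln(141.6/60)/0.5) = Φ(1.717) = 95.7%, so 4.3% of controls are lost as well. TCD mean = 67.99 x Φ(1.645 - 0.5)/0.95 + 5 = 67.54. Control mean = 67.99 x Φ(1.717 - 0.5)/0.957 = 63.10. Difference +4.4.
2. *TCD losses at random in the slower half, no controls lost.* Slower-half mean before the delay = 67.99 x Φ(0.5)/0.5 = 94.02. TCD mean = (67.99 - 0.05 x 94.02)/0.95 + 5 = 71.62. Difference +3.6.
3. *Only the slowest TCD subjects lost, no controls.* 67.54 - 67.99 gives -0.4.

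For the 90-minute percentage, the TCD figure is 75.7/0.95 = 79.7% among the punctured in cases 1 and 3. In case 1 the control figure is 79.1/0.957 = 82.7%. In case 2, one in ten of the slower half is lost, so the all-randomised TCD figure is 50 + 0.9 x 25.7 = 73.1% and the punctured-only figure is 73.1/0.95 = 77.0%.

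| Case | Mean difference, punctured only (true +5) | Within 90 min, punctured only: TCD v control | Within 90 min, all randomised: TCD v control |
|---|---|---|---|
| 1 | +4.4 min | 79.7% v 82.7% | 75.7% v 79.1% |
| 2 | +3.6 min | 77.0% v 79.1% | 73.1% v 79.1% |
| 3 | -0.4 min | 79.7% v 79.1% | 75.7% v 79.1% |

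Simulating the same model agrees to within about 0.1 min (for example +4.5 and +3.7 in cases 1 and 2).

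**Wider range, common cutoff in both arms.** Medians of 60 or 90 min, log-SD 0.4 or 0.6 and cutoffs of 120, 150 or 180 min were tried. Section 4.16.1 allows a NovaGuide session of up to 20 + 20 = 40 min, so delays up to 40 min were included. Among punctured subjects a true 10-min delay shows as 6.3 to 9.9 min, 20 min as 12.1 to 19.6, and 40 min as 22.1 to 38.7. The bias was toward no harm every time, and the delay was never fully hidden. In one case (median 60, log-SD 0.6, 20-min delay, cutoff 120) the time difference reads 15.4 min while 80.3% of TCD subjects and 87.6% of controls are punctured. The plan would not report that second contrast.

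**The case against.** Much of the case on the other side stands.

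- *A reader might infer that the plan excludes unpunctured subjects.* It does not say so; it is silent. A time that does not exist drops out by default, but the defect is a missing rule.
- *A reader might infer that the 90-minute percentage has thrombectomy recipients as its denominator.* The parenthesis can also be read as a percentage of all acute ischaemic stroke patients, which would count a lost case as a failure. The denominator is ambiguous. The time endpoints in sections 4.2.1 and 4.2.2 are the firmer ground, because they are conditional on puncture under either reading.
- *A reader might infer that a real delay could be reported as no delay or as an advantage.* In these calculations that needs the slowest TCD subjects to be lost and no controls. If time running out is what costs a thrombectomy, slow controls lose it too, and the delay is then shrunk but not erased.
- *Safeguards exist.* Anticipated insufficient time is an exclusion, the scan may be ended at any point, and measurements are not to delay care (sections 4.6, 4.16). These make a lost thrombectomy less likely. They are instructions for conduct, though, and the endpoint exists to test whether they worked.
- *No decision turns on these times.* The stated success criteria are AUC, sensitivity and specificity (sections 11.1, 11.2, 11.5), and the workflow comparison has no margin or alpha. This lowers the severity but does not remove the gap in a listed primary safety endpoint.

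**Conclusion.** The concern holds as a missing analysis rule. The two puncture times are conditional on an event after randomisation that the scan could affect. The plan neither counts subjects without that event nor compares its frequency between arms, and it further restricts the section 11.1 metrics to subjects with NovaGuide measurements. If any thrombectomy is lost through scanning, the comparison with Cohort C leans toward no harm; if none is lost, this bias does not arise.

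The size is unknown, because the documents give neither a thrombectomy rate nor a time distribution. Under the assumed model a true 5-min delay reads as +4.4, +3.6 or -0.4 min depending on who is lost, and the last value is an extreme case. Should-fix: the endpoint carries the no-delay claim, but no stated success criterion depends on it.

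**What to change.** Before comparative workflow data are seen, specify the following for all randomised LVO subjects (Cohort A against Cohort C), by assigned arm and regardless of whether a NovaGuide measurement was obtained:

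1. The proportion reaching groin puncture, with the difference between arms and its confidence interval.
2. The percentage punctured within 90 minutes of arrival, with all randomised LVO subjects as denominator and no puncture counted as not reached. Give the punctured-only version beside it for the benchmark comparison.
3. CTA-to-puncture as cumulative incidence of puncture to a fixed, pre-stated horizon, with unpunctured subjects retained as not reached.

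Keep the punctured-only times as descriptive.

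The cost is mostly SAP wording. Section 4.18 already collects workflow times and randomisation assignment. It lists no reason for the absence of a puncture, so one CRF field may be needed to interpret the results. Cohort A does not require that thrombectomy be planned, so subjects for whom it never was will dilute the all-randomised percentages. The amount is unknown, but in expectation it is equal in both arms.

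The puncture proportion will be imprecise. Power for an assumed 90% against 80% (two-sided 0.05) is about 31% at 54 per arm and 70% at 156 per arm. A formal non-inferiority claim with an assumed 10-point margin (one-sided 0.025, 80% power) would need 142 per arm at a 90% rate or 252 per arm at 80%. It is best reported as an estimate with its interval unless a margin is set and justified.

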11.2 Phase 2 Statistical Analysis

Primary Endpoint Analysis: Demonstration of VCI biomarker performance at or exceeding 90% ROC-AUC (targeting SEN & SPE greater than 90%) to standard of care imaging across multiple centers.

Here, we will determine the final biomarker performance using the dataset collected and reviewed by the core lab. Similar analyses will be run on the VCI biomarker distributions for the Phase 2 subject group as was done in Phase 1. Additionally, subgroup analyses comparing biomarker results across research sites, and age groups, will be conducted to determine if any age or NovaGuide inter-operator variability effects are present in the data (two-way ANOVA with post-hoc comparisons).

Sample size calculation: In Phase 2, we seek to demonstrate stricter confidence bounds on biomarker diagnostic performance in excess of 90% ROC-AUC. Assuming the biomarker is observed to meet that performance threshold, then a sample of approximately 150 LVO subjects in each patient group is required to attain a one-tailed 95% confidence bound on the observed AUC of 3%. That is, the target AUC and sample size would afford 95% confidence that the underlying general population AUC is greater than 87%. Moreover, across five sites, this results in approximately 30 LVO subjects per site, affording sufficient power for detection of moderate potential inter-site effects in the range of Cohen’s $D \geq 0.75$.

Calculate study and site specific stroke workflow times: Stroke workflow parameters and times are well characterized in literature, including “Get with the Guidelines, Stroke” published by the American Heart Association, Inc. and will be utilized as a historical control comparator for data collected in Phase 2. We will use these published stroke guidelines which have mean times for the stroke workflow parameters to show that we are non-inferior to these when using the NovaGuide device. Additionally, the data will be compared to the corresponding randomized group (Cohort C and D)

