2 BACKGROUND AND RATIONALE OF STUDY

The incidence of Large Vessel Acute Ischemic Stroke (AIS) has been estimated to be approximately 250,000 patients per year in the United States and is the leading cause of disability and fifth leading cause of death. Although endovascular interventions (stentriever) and pharmaceutical (tPA) treatments exist for large vessel occlusion (LVO), their use is limited due to the short time window from symptom onset during which these treatments are indicated to be administered. Moreover, recent estimates suggest only approximately 10% of eligible patients receive interventional treatment which has shown to lead to better outcomes in several world-wide RCTs. Currently, the gold standard for stroke diagnosis is CT angiogram (CTA) which is limited to in-hospital use or a low number of mobile stroke ambulances, all costing multi-millions of dollars, requiring expert operators and IV injection of iodine-rich contrast material. Additionally, the clinical stroke assessment scales (RACE, LAMS, CPSS) used in the field, although low cost and non-invasive, have proven unreliable due to training requirements and low inherent accuracies, with SEN and SPE ranging in a recent study from 0.50-0.64 and 0.83-0.92, respectively[13,14]. In order for intervention to be successful, a standardized, quantitative, field based (prehospital and pre-CTA) diagnostic tool is needed to improve LVO identification and ensure rapid transfer to a capable medical facility.

Goals. Establish clinical viability of a fully automated, non-invasive transcranial Doppler (TCD) derived biomarker based on cerebral hemodynamics for prehospital LVO assessment.

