11 STATISTICAL ANALYSIS

11.1 Phase 1 Statistical Analysis:

Primary Endpoint Analysis: Demonstration of VCI diagnostic performance at or exceeding 85% ROC-AUC (targeting SEN greater than 90%) to standard of care imaging.

Biomarker Validation and Analysis: VCI will be computed for each subject according to the procedure outlined in section 3.5, and group differences will be assessed using appropriate statistical methods. ROC-AUC will be computed detailing separability between groups for comparison to standard of care imaging (CTA) and prehospital/neurological clinical scales, along with SEN, SPE, and accuracy at various levels of diagnostic threshold, including that corresponding to Youden's maximal J-statistic.

Sample size calculation: From the results of our feasibility study, we estimate that expected effect size between VCI distributions for LVO (cohort A) and IHC groups (cohort B) will be large (Cohen's $D > 1.25$), such that only a small number of subjects in each group ($N = 11$) will be sufficient to detect significant differences (alpha of 0.05) with standard statistical power of 80%. However, in Phase 1 we seek to demonstrate the stronger aim of biomarker diagnostic performance in excess of 85% ROC-AUC. Assuming this target AUC is met, then sample size determines the confidence bounds on that estimate. In Phase 1 we require a sample of sufficient size to power confidence in the superiority of VCI diagnostic performance relative to current clinical prehospital stroke assessment scales. As existing preclinical scales top out at 78% AUC, this can be accomplished with a sample of roughly 50 subjects in each patient group, which gives a one-tailed 95% confidence bound on the target 85% AUC of less than 7%. The specification of 54 subjects per group is a target number intended to guarantee acquisition of a sufficient sample assuming at least 90% of target enrollment.

Initial safety endpoint analysis: Throughout the study we will collect adverse events, which will be used to determine the safety of the device within the acute stroke environment. In our EXPEDITE study which is also run in the ER for stroke assessment, the device has been designated minimal risk by the IRB and we have not had any serious adverse events in over 80 subjects. We will continue to closely monitor this metric.

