11.5 Data Analysis

Evaluation of correlation between diagnostic imaging standard of care and VCI biomarker by an independent core laboratory masked to local radiology determination. Success criteria will include clinical validation of VCI biomarker for LVO detection threshold performance at or exceeding 90% ROC-AUC (targeting SEN & SPE greater than 90%) to standard of care imaging.

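### The Phase 2 success criterion sets an AUC floor of 90% beside a target of SEN and SPE both above 90%, but under usual ROC shapes 90/90 needs an AUC of about 0.96

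*Combined protocol and SAP*

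**What the plan says.** Section 11.2 gives the Phase 2 primary analysis as showing VCI "performance at or exceeding 90% ROC-AUC (targeting SEN & SPE greater than 90" per cent). Section 11.5 repeats this and names it as the standard for success: "Success criteria will include clinical validation of VCI biomarker for LVO detection threshold performance at or exceeding 90% ROC-AUC", with the same parenthesis on SEN and SPE. The Data Analysis row of the synopsis matches 11.5.

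Section 4.2.2 treats all three measures jointly as primary in the pivotal phase: "Area Under the Curve (AUC), Sensitivity, and Specificity of VCI when compared against standard of care CTA imaging for large vessel occlusion assessment".

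The Phase 2 sample size rests on AUC alone. Section 11.2 asks for "a sample of approximately 150 LVO subjects in each patient group" to obtain a "one-tailed 95% confidence bound on the observed AUC of 3" per cent, so that an observed AUC of 90% supports a population AUC above 87%. Planned enrolment in the TCD arm is 156 per cohort.

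No section says whether the SEN/SPE target is binding, fixes the VCI cut-off at which it is judged, or gives a confidence bound or sample size for SEN or SPE. Section 11.1 reports SEN and SPE at several cut-offs, including the one that maximises Youden's J, and 11.2 carries similar analyses into Phase 2.

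**The concern.** The criterion reads as though an AUC of 90% and SEN and SPE above 90% describe the same marker. AUC averages performance over all cut-offs, while SEN and SPE describe a single cut-off. A continuous marker needs an AUC well above 0.90 before any cut-off gives 90% on both.

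Phase 2 is the pivotal phase, and section 2 says its data are meant to support a regulatory submission, so the meaning of success matters. As written, a marker near the AUC floor can pass while its best balanced accuracy implies miss and false-alarm rates of about 18% each, against a printed target of under 10%. The opposite reading is no better: if the target binds, the value at which the study was planned cannot deliver it.

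**Working it through.** **Inputs.** AUC floor 0.90 and SEN/SPE target above 0.90 (11.2, 11.5, synopsis); about 150 per group, one-sided 95% bound of 3%, lower limit 87% (11.2); 156 per cohort (4.4). The documents give no distribution for VCI, so the shape of the ROC curve is an assumption and is varied below.

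**1. The plan's own figure.** Hanley–McNeil standard error at A = 0.90 with n = 150 per group:
- Q1 = A/(2 − A) = 0.8182; Q2 = 2A²/(1 + A) = 0.8526; A² = 0.81.
- Variance = [0.09 + 149 × 0.0082 + 149 × 0.0426]/150², computed with unrounded terms, so SE = 0.01845.
- 1.645 × SE = 3.04%; lower limit 0.8696.

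With 156 per group the half-width is 2.98% and the limit 0.8702. The stated 3% and 87% reproduce. The fault is not in this calculation.

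**2. A bound that needs no normality.** A concave ROC curve through the point (1 − SPE, SEN) lies on or above the two straight lines joining that point to (0,0) and (1,1). The area under those lines is (1 − SPE) × SEN/2 + SPE × (SEN + 1)/2 = (SEN + SPE)/2. So AUC ≥ (SEN + SPE)/2. If both exceed 0.90, AUC must exceed 0.90; at AUC exactly 0.90 they cannot both do so.

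**3. Equal-variance binormal model.** AUC = Φ(d/√2), and at the balanced cut-off SEN = SPE = Φ(d/2).
- AUC 0.90: d = √2 × 1.2816 = 1.812, so SEN = SPE = Φ(0.906) = 81.8%. Holding SEN at 90% leaves SPE = Φ(1.812 − 1.2816) = 70.2%.
- AUC 0.87 (the plan's lower limit): d = 1.593, so SEN = SPE = 78.7%.
- 90/90: d = 2 × 1.2816 = 2.563, so AUC = Φ(2.563/√2) = 0.965.

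**4. Other shapes.** With SD ratio b, SEN = SPE = Φ(z₀.₉₀ × √(1 + b²)/(1 + b)) at AUC 0.90, and 90/90 needs AUC = Φ(z₀.₉₀ × (1 + b)/√(1 + b²)).

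| Model | SEN = SPE at AUC 0.90 | AUC needed for 90/90 |
|---|---|---|
| Binormal, b = 1 | 81.8% | 0.965 |
| Binormal, b = 0.5 or 2 | 83.0% | 0.957 |
| Binormal, b = 0.25 or 4 | 85.5% | 0.940 |
| Bilogistic | 83.1% | 0.957 |
| Power-law ROC | 82.4% | 0.956 |

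Because √(1 + b²) < 1 + b for every positive b, no binormal marker with AUC 0.90 reaches 90/90.

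**5. Chance of meeting each part.** Simulation with 156 per group, equal-variance binormal, 5,000 runs per row. The cut-off is the best one in the same data, which favours the marker.

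| True AUC | Observed AUC ≥ 0.90 | Some cut-off with SEN and SPE both > 90% |
|---|---|---|
| 0.90 | 51% | 0% |
| 0.92 | 90% | 0.04% |
| 0.95 | 100% | 11% |
| 0.965 | 100% | 51% |
| 0.975 | 100% | 86% |
| 0.98 | 100% | 96% |

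**The case against.** The strongest defence is that the parenthesis is an aspiration and the AUC figure is a floor. A marker with AUC of 0.965 or more is compatible with both parts. This stands as far as it goes: the target is out of reach only for markers at or near the floor. But the target sits inside the success criterion, SEN and SPE are named primary endpoints, and the study is planned at 0.90, so their status has to be stated.

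The 82% figure is model-based. That is right, and it should always be quoted with its model. The concave bound does not need normality. Without concavity, a 90/90 point forces only AUC ≥ 0.90 × 0.90 = 0.81, so an irregular ROC curve could escape the bound.

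Three stronger readings are tempting but not supported:

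- **That an 82%/82% marker would be reported as validated above 90%.** Observed SEN and SPE are to be reported, and the only 90% pass mark is labelled as AUC.
- **That Phase 1 has the same conflict.** Section 11.1 asks for "VCI diagnostic performance at or exceeding 85% ROC-AUC (targeting SEN greater than 90" per cent) and sets no SPE target. Some cut-off gives SEN of 90% at any AUC.
- **That VCI at AUC 0.85 would be less specific than the field scales.** Section 2 describes those scales "with SEN and SPE ranging in a recent study from 0.50-0.64 and 0.83-0.92, respectively", so the high SPE goes with low SEN. Under the same model with d = 1.466, VCI would have SPE of about 0.87 at SEN 0.64 and 0.93 at SEN 0.50.

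**Conclusion.** The concern holds for Phase 2. The two parts of the success criterion are different performance levels. Under the equal-variance binormal model, AUC 0.90 means SEN and SPE of about 82% (82–83% for SD ratios of 0.5 to 2, up to 85.5% at a ratio of 4). Reaching 90/90 takes an AUC of about 0.96 (0.94 at a ratio of 4). That both cannot exceed 90% at AUC 0.90 holds for any concave ROC curve.

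A marker at or just above the floor can therefore pass on AUC, in 51% of trials at true AUC 0.90 and 90% at 0.92, with essentially no chance of reaching the SEN/SPE target. If that target binds, the planning value of 0.90 gives essentially no chance of success. The simulated percentages assume the equal-variance model and that the AUC pass mark applies to the observed value. Section 11.2 suggests the latter but does not state it as a rule.

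**What to change.** In the synopsis, 11.2 and 11.5:

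1. Keep AUC of at least 90% as the success criterion.
2. Take the SEN/SPE target out of it, or label it explicitly as a non-binding goal.
3. State that, under a binormal model, AUC 0.90 implies SEN and SPE of about 82%, and 90/90 implies an AUC of about 0.96.

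This changes wording only, with no effect on patients or procedures. The price is a less favourable stated accuracy. It should be settled before Phase 2 data are analysed.

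If the sponsor wants SEN and SPE to be binding, wording is not enough. That limb needs a pre-specified VCI cut-off and its own sample-size justification: with 156 per group, the chance of observing both above 90% is only about 51% even at true AUC 0.965, and that uses the most favourable cut-off. No change to 11.1 is needed on this point.
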